5.8 Independent Data Monitoring Committee (DMC)

A DMC will be established to provide independent review of safety data and to assure that the risk to patients is minimized. The DMC will operate in accordance with a signed charter and will be composed of 2 oncologists familiar with clinical use of the study drugs and an ad hoc independent, knowledgeable biostatistician.

Safety data will be collected and monitored on an ongoing basis throughout the study. IMDZ will summarize all available safety and laboratory data on all patients at regular intervals (at least every 3 months) during the study, as specified in the DMC charter. IMDZ and the DMC will conduct separate reviews of these data for any safety trends that might impact the treatment of patients. Safety issues that arise out of such ongoing reviews could lead to modifications of the treatment program.

The unblinded DMC will review all cumulative safety information from the Safety Run-In prior to recommendations for further patient enrollment (Section 5.4.1). All related and unexpected (i.e., expedited) SAEs and DLTs will be reviewed as individual cases arise; related and unexpected SAE reports will be expedited to regulatory authorities, investigators, and DMC members. DLTs and SAEs considered at least possibly related to study regimen will be reviewed by the DMC and the Sponsor as they are reported and on an ongoing basis. These reviews may lead to modification or stopping of the treatment program if related, treatment-emergent adverse events indicate a safety profile that is inconsistent or significantly worse than reported with the use of either CMB305 or atezolizumab alone. The DMC will also perform periodic reviews of all AEs, laboratory results, and patient discontinuations.

The DMC may convene on an ad-hoc basis to evaluate any urgent safety issues. Upon request, the DMC will be granted access to any available data pertinent to the issues under evaluation. IMDZ will provide cumulative data, as specified in the DMC charter, to the DMC for review.

5.9 Archival Tissue

A representative formalin-fixed paraffin embedded (FFPE) archival tumor specimen collected at first diagnosis and/or subsequent tumor recurrence(s) consistent with the patient's diagnosis is required for NY-ESO-1 diagnosis and participation in this study. A minimum of 8 unstained serial sections are needed. Documentation of NY-ESO-1 expression in prior tumor samples may have been collected from any procedure performed before baseline activities. There is no time limit for use of the results from the IMDZ-approved central lab.

In addition, a pre-treatment tumor sample (FFPE block [preferred] or a minimum of 17 unstained serial sections, including 5 slides at 4 μm and 12 slides at 7 μm) should be derived from a fresh biopsy or a prior resection/biopsy performed ≤ 6 months prior to screening for immune analysis. This specimen must be accompanied by the associated pathology report. Fine-needle aspiration, brushing, cell pellet from pleural effusion, and lavage samples are not acceptable. Tumor tissue from bone metastases is not evaluable for tumor PD-L1 expression and is therefore not acceptable. For core needle biopsy specimens, at least three cores should be submitted for evaluation.

For samples not meeting minimum requirements for size/slide number, contact the Medical Monitor via your site contact with information on tissue size and tumor content/number of slides to determine eligibility.

Alternatively, or if the archival tumor sample does not meet minimum requirements, the patient may be offered the option of undergoing a pretreatment procedure (excisional or core tumor biopsy) to obtain an adequate tumor sample. Acceptable samples include core needle biopsies for deep tumor tissue (minimum 3 cores) or excisional, incisional, punch, or forceps biopsies for cutaneous, subcutaneous (SC), or mucosal lesions. A similar biopsy will be taken for specimens on Day 42, on Day 98 (± 2 weeks), at 6 months or longer (for patients with treatment response), and at the time of progression.

6.0 SELECTION AND WITHDRAWAL OF PATIENTS

This study plans to enroll patients with locally advanced, relapsed, or metastatic sarcoma whose tumor expresses the NY-ESO-1.

Patient eligibility criteria in the proposed trial have been designed to ensure that the enrolled patients are adequately healthy to tolerate investigational therapy, ill enough to be appropriate for investigational therapy, and have sufficiently low tumor burden or indolent disease to be appropriate for a vaccine therapy. Potential risks include injection site reactions and systemic AEs, which could include immunologically-related AEs. Safety monitoring will be intensive and comprehensive with careful monitoring for acute adverse reactions and includes regular reviews by an independent DMC.

6.1 Inclusion Criteria

Patients must meet ALL of the following criteria to be enrolled in the study:

1. Locally advanced, relapsed, or metastatic sarcoma with measurable tumor burden following therapy, as defined by RECIST v1.1; the total of all lesions must be ≤ 12 cm (for synovial sarcoma) or ≤ 15 cm (for myxoid/round cell liposarcoma [MRCL])
2. Tumor histology consistent with synovial sarcoma or MRCL
3. Tumor specimen positive for NY-ESO-1 expression by IHC
4. Inadequate response, relapse, and/or unacceptable toxicity with one or more prior systemic, surgical, or radiation cancer therapies
5. Have resolution of toxic effect(s) of the most recent prior therapy to Grade 1 or less (except Grade 2 or less neuropathy or alopecia). If subject received major surgery or radiation therapy, they must have recovered from the toxicity and/or complications from the intervention.
6. ≥ 18 years of age before the first scheduled dose
7. Eastern Cooperative Oncology Group (ECOG) performance status of 0 or 1
8. Electrocardiogram (ECG) without evidence of clinically significant abnormality
9. If female of childbearing potential (FCBP), willing to undergo pregnancy testing and agrees to use at least 2 adequate barrier contraceptive methods during the dosing period and for 90 days after the last injection of CMB305 or atezolizumab
10. If male and sexually active with a FCBP, must agree to use highly effective contraception such as latex condom during the dosing period and for three months after last CMB305 injection
Note: Abstinence is acceptable for either gender if this is the established and preferred contraception for the subject.

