Inclusion Criteria	
 1. Locally advanced, relapsed, or metastatic sarcoma with measurable tumor burden following therapy, as defined by RECIST v1.1; the total of all lesions must be ≤ 12 cm (for synovial sarcoma) or ≤ 15 cm (for myxoid/round cell liposarcoma [MRCL]). 2. Tumor histology consistent with synovial sarcoma or MRCL. 3. Tumor specimen positive for NY-ESO-1 expression by IHC. 4. Inadequate response, relapse, and/or unacceptable toxicity with one or more prior systemic, surgical, or radiation cancer therapies. 5. Have resolution of toxic effect(s) of the most recent prior therapy to Grade 1 or less (except Grade 2 or less neuropathy or alopecia). If subject received major surgery or radiation therapy, they must have recovered from the toxicity and/or complications from the intervention. 6. ≥ 18 years of age before the first scheduled dose. 7. Eastern Cooperative Oncology Group (ECOG) performance status of 0 or 1. 8. ECG without evidence of clinically significant abnormality. 9. If female of childbearing potential (FCBP), willing to undergo pregnancy testing and agrees to use at least 2 adequate barrier contraceptive methods during the dosing period and for 90 days after the last injection of CMB305 or atezolizumab. 10. If male and sexually active with a FCBP, must agree to use highly effective contraception such as latex condom during the dosing period and for three months after last CMB305 injection. Note: Abstinence is acceptable for either gender if this is the established and preferred contraception for the subject.
Exclusion Criteria	
 1. Investigational therapy within 4 weeks prior to CMB305 dosing. 2. Prior administration of other NY-ESO-1-targeting immunotherapeutics. 3. Prior treatment with CD137 agonists or immune checkpoint blockade therapies, including anti-CTLA-4, anti PD-1, and anti PD-L1 therapeutic antibodies, or any other antibody or drug targeting T-cell costimulation. 4. Treatment with systemic immunostimulatory agents (including but not limited to interleukin-2) within 4 weeks or five half-lives of the drug, whichever is shorter, prior to first dose. 5. Significant immunosuppression from:

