- h. An HIV screening test will be repeated on Day 168 to determine if seroconversion has occurred following LV305 injections. If positive, further testing can demonstrate that the normal complement of HIV proteins is not present (unless the patient has developed a true HIV infection).
- i. Blood for immunogenicity will be collected at clinical sites that are trained in peripheral blood mononuclear cells (PBMC) isolation. Baseline samples will be drawn twice to ensure a good yield. At least 55 mL should be collected in 8 Cell Preparation Tubes (CPT)TM tubes for T-cell response assays. See the Lab Manual for processing details.
- j. Initial safety labs are to be performed within 4 days before treatment initiation. On treatment days during the study dosing period, the hematology and clinical chemistry laboratories must also be performed and reviewed before dosing and may be performed up to 48 hours prior to the planned dosing.
- k. Thyroid function tests (triiodothyronine [T₃], thyroxine [T₄], and thyroid stimulating hormone [TSH]) should be taken at initial screening and at least every 3 months while being treated with atezolizumab. As thyroid disorders could occur at any time as a result of atezolizumab treatment, patients should be monitored for changes in thyroid function for clinical signs and symptoms of thyroid disorders (at the start of treatment, periodically during treatment, and as indicated based on clinical evaluation).
- l. Urine pregnancy test must be performed for women of childbearing potential within 72 hours before study drug administration and negative before study drug administration, including during the follow-up period if patients are still receiving booster doses of G305 and/or atezolizumab. Serum pregnancy test may be performed if the site's standard operating procedures allow.
- m. Booster doses of G305 will be given 6 weeks following the Day 84 dose and every 6 weeks thereafter for 1 year (from Day 0) or until disease progression at the staging visits.
- n. Atezolizumab should be continued every 3 weeks for 2 years (from Day 0) or until progression unless toxicity occurs.

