- m. The pre-treatment biopsy must be completed ≤ 6 months prior to screening; if not available, a fresh biopsy may be included in the screening process. The tissue biopsy taken on Day 98 can be performed ± 2 weeks from this study visit; however, the patient may opt out of the Day 98 biopsy after a discussion with a physician and documentation in the patient's chart. If a tumor biopsy is not feasible, a biopsy may be done at a subsequent visit with approval provided by the Sponsor.
- n. Once patients have progressed and study drugs are discontinued for more than 30 days, their physicians will be contacted by the sites every 3 months by telephone until the study is completed (last patient, last death in the study) to assess OS. The attending physician will be contacted quarterly until study completion for identification of subsequent treatments and survival status.

Figure 1 Dosing Schedule for Each Treatment Arm

A. Combination Treatment Arm

B. Control Arm

Abbreviations: PBMC = peripheral blood mononuclear cell; CPI = checkpoint inhibitor.

Red syringe = LV305 injections; Green arrows = G305 injections; blue antibodies indicate atezolizumab treatment days.

The combination treatment arm will consist of administration of CMB305 and atezolizumab (A). Dosing of CMB305 (LV305 and G305) will occur every 2 weeks beginning with the administration of 2 consecutive doses of LV305 followed by alternating administration of G305 and LV305 for 12 weeks (i.e. during the Treatment Phase). Atezolizumab will be administered every 3 weeks. The control arm (B) will receive atezolizumab alone every 3 weeks.

Note: For the combined treatment arm (A), the trial will be conducted in 4 phases: Treatment Phase (study Days 0 to 84), Booster Phase (post Day 84 to 1 year post Day 0), Maintenance Phase (from 1 year to 2 years post Day 0), and Survival Follow-up Phase (quarterly thereafter). For the control arm (B), the trial will be conducted in 3 phases: Treatment Phase (study Days 0 to 84), Maintenance Phase (post Day 84 to 2 years post Day 0), and Survival Follow-up Phase (quarterly thereafter). Dosing with atezolizumab may continue up to 2 years until confirmed progression in both treatment arms. G305 may be given every 6 weeks following the Day 84 dose for up to 1 year (from Day 0) as a booster injection during the restaging follow-up visits.

TABLE OF CONTENTS

INVESTIGATOR AGREEMENT PAGE	2
STUDY SYNOPSIS	4
TABLE OF CONTENTS	22
LIST OF TABLES	27
LIST OF FIGURES	27

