7.5.2 Contraception

Animal reproduction studies have not been conducted with CMB305 to evaluate the effect of the components on reproduction or fetal development. Atezolizumab may have adverse effects on a fetus *in utero* and it is not known if atezolizumab therapy has any adverse effects on the composition of sperm. Furthermore, human IgGs are known to cross the placental barrier and the PD-1/PD-L1 pathway has been linked with pregnancy maintenance.³¹

Currently, there is no human data demonstrating the effects of this line of CPI therapy in pregnancy, lactation, or reproductive potential. Therefore, non-pregnant, non-breast-feeding women may only be enrolled into the trial if they are willing to use 2 methods of birth control or are considered highly unlikely to conceive. Highly unlikely to conceive is defined as:

1. Surgically sterilized,
2. Postmenopausal (a woman who is ≥ 45 years of age and has not had menses for greater than 1 year will be considered postmenopausal), or
3. Not heterosexually active for the duration of the study.

The 2 birth control methods can be either 2 barrier methods, or a barrier method plus a hormonal method to prevent pregnancy. Subjects should start using birth control from Study Visit 1 throughout the study period up to 90 days after the last dose of study therapy.

The following are considered adequate barrier methods of contraception: diaphragm, condom (by the partner), copper intrauterine device, sponge, or spermicide as per local regulations or guidelines. Appropriate hormonal contraceptives will include any registered and marketed contraceptive agent that contains an estrogen and/or a progestational agent (including oral, SC, intrauterine, or IM agents).

Subjects should be informed that taking the study medication may involve unknown risks to the fetus (unborn baby) if pregnancy were to occur during the study. In order to participate in the study, they must adhere to the contraception requirement (described above) for the duration of the study and during the follow-up period. If there is any question that a patient will not reliably comply with the requirements for contraception, that patient should not be entered into the study.

It is unknown whether atezolizumab or any components of CMB305 are excreted in human milk. Since many drugs are excreted in human milk, and because of the potential for serious adverse reactions in the nursing infant, subjects who are breast-feeding are not eligible for enrollment.

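### Inclusion criterion 10 ties men's post-dose contraception to the last CMB305 injection and omits atezolizumab, so it can end up to 90 days before the section 7.5.2 date

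*Protocol*

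**What the plan says.** - **Men, criterion 10 (protocol 6.1).** A man who is sexually active with a woman of childbearing potential "must agree to use highly effective contraception such as latex condom during the dosing period and for three months after last CMB305 injection". The synopsis sets the same end point, "for three months after last CMB305 injection". Neither place names atezolizumab.
- **Women, criterion 9 (protocol 6.1).** The commitment covers the dosing period and continues "for 90 days after the last injection of CMB305 or atezolizumab". Both drugs are named.
- **Treatment by arm.** The Figure 1 legend says: "The control arm (B) will receive atezolizumab alone every 3 weeks". For the combination arm, Table 1 footnote m says: "Booster doses of G305 will be given 6 weeks following the Day 84 dose and every 6 weeks thereafter for 1 year", counted from Day 0. Footnote n says: "Atezolizumab should be continued every 3 weeks for 2 years (from Day 0) or until progression unless toxicity occurs". Table 2 footnote l gives the control arm the same two-year atezolizumab schedule.
- **Section 7.5.2.** It says that "it is not known if atezolizumab therapy has any adverse effects on the composition of sperm". It tells subjects, without stating sex, to use birth control from the first study visit "throughout the study period up to 90 days after the last dose of study therapy".
- **Section 9.4.9.** It sets a 90-day period after atezolizumab for women of childbearing potential. It requires birth control of sexually active men while the study runs, but states no post-dose period for them.

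**The concern.** The drug whose effect on sperm the protocol calls unknown is the one missing from the men's eligibility criterion. In the control arm it is the only study drug, so the event that starts the three-month clock never happens. In the combination arm CMB305 ends within a year while atezolizumab can run for two, so the three months can expire while the man is still being dosed.

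Criterion 10 is the commitment a site checks at screening. A site working from it could tell a control-arm man that his obligation ends with his last infusion. A site working from 7.5.2 would name a date 90 days later. What is at stake is consistent advice about possible partner and fetal exposure. Efficacy and statistical conclusions are not involved.

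**Working it through.** The protocol gives no calendar end date of its own to reproduce, so the check is date arithmetic on the nominal schedule.

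**Inputs**
- G305 boosters (Table 1, footnote m): Day 84 + 42k, up to Day 365. The largest k is 6, so the last booster is 84 + 42 × 6 = Day 336.
- Atezolizumab (Table 1, footnote n; Table 2, footnote l): Day 21k, up to Day 730. The largest k is 34, so the last dose is 21 × 34 = Day 714.
- Three months is taken as 91 days (3 × 30.4375, rounded).
- The dosing period is not defined. It is taken to run to the last dose of any study drug, which is the reading most favourable to the protocol.

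**End dates**
- Section 7.5.2: last dose of any study drug + 90.
- Criterion 10: the later of the last dose of any study drug and the last CMB305 dose + 91. With no CMB305, it is the last dose itself.
- Shortfall: the 7.5.2 date minus the criterion 10 date, set to 0 if negative.

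**Control arm.** With the last atezolizumab dose on Day t, the shortfall is (t + 90) − t = 90 days at any stopping time. On the full schedule, criterion 10 ends on Day 714 and 7.5.2 on Day 804.

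**Combination arm, all boosters given.** The three months end on Day 336 + 91 = Day 427. With the last atezolizumab dose on Day t, the shortfall is max(0, (t + 90) − max(t, 427)):

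| Last atezolizumab dose (Day t) | 7.5.2 ends | Criterion 10 ends | Shortfall (days) |
|---|---|---|---|
| 336 | 426 | 427 | 0 |
| 357 | 447 | 427 | 20 |
| 378 | 468 | 427 | 41 |
| 399 | 489 | 427 | 62 |
| 420 | 510 | 427 | 83 |
| 441 | 531 | 441 | 90 |
| 714 | 804 | 714 | 90 |

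**Combination arm, both drugs stopped earlier on the nominal schedule.** The shortfall is 0 when both are last given on the same day. It is 6 when CMB305 was 7 days earlier (for example Day 21 against Day 14: 111 − 105). It is 20 when CMB305 was 21 days earlier (for example Day 105 against Day 84: 195 − 175).

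**Check on the fix.** If criterion 10 ran to 90 days after the last dose of either drug, the shortfall would be 0 in both arms.

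**The case against.** The strongest reply is that sites apply the whole protocol, not one criterion. Section 7.5.2 speaks to all subjects, makes its contraception rule a condition of taking part, and already runs to 90 days after the last dose. Section 9.4.9 names men. If the rules are cumulative, the longer one governs and no man is left without cover. In that case the figures above measure an inconsistency between sections, not an unprotected period.

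That is a fair limit, but it does not remove the problem. Most of 7.5.2 concerns women: it leads in with the conditions for enrolling women, and its accepted methods include a condom used by the partner. Its application to men rests on the word for subjects and on the sperm statement. The 90-day atezolizumab rule in 9.4.9 is expressly for women. The provision written specifically for men is criterion 10, and it gives the earlier date.

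It can also be said that tying the men's period to CMB305, a gene-transfer product, was deliberate. The documents do not say so. Two further points stand. Partner pregnancies must be reported under 9.4.9, although reporting detects exposure and does not prevent it. The consent text is not available for review, so what men are actually told is unknown.

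The day-level figures ignore visit windows and the permitted one-week atezolizumab delays. These would move individual values by days, but would not change the 90-day maximum or the control-arm result.

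**Conclusion.** The point holds as a minor wording fault. Criterion 10 gives control-arm men no post-dose period. For combination-arm men it ends 0 to 90 days before the 7.5.2 date. Both statements assume that the dosing period includes atezolizumab. If it meant CMB305 only, the full-schedule combination gap would be 804 − 427 = 377 days and the control arm would have no defined end, but the term is not limited to CMB305 and the conclusion does not rely on that reading. The number of men affected cannot be derived from the documents.

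Three stronger inferences are not supported:
- **That men need 90 days.** Section 7.5.2 says only that the effect on sperm is unknown, and the rationale in 9.4.9 is maternal-fetal tolerance. The case is for one consistent end date.
- **That a third end date, study completion, competes with the other two.** A reader might get there by joining the 9.4.9 requirement on men to the survival follow-up described in 5.7, or from the reference to a follow-up period in 7.5.2. But Table 1 footnote l and Table 2 footnote k use that term for time still on treatment. Section 5.1 puts expected participation at up to 2.1 years before survival follow-up, and 7.5.2 itself stops at 90 days after the last dose.
- **That the pregnancy windows in 9.4.1 and 9.4.9 conflict.** The first governs reporting. The second governs discontinuation and outcome follow-up. They need not match.

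No endpoint, sample size or analysis is affected.

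**What to change.** In criterion 10, in both 6.1 and the synopsis, require men's contraception through the dosing period and for 90 days after the last dose of CMB305 or atezolizumab, whichever is later. In 7.5.2, state that the 90-day period applies to male and female subjects. Align the consent text.

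The cost is a wording amendment, with no new procedures or patients. The downside is that men commit to contraception for up to 90 days longer than criterion 10 now states.

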6.2 Exclusion Criteria

Patients meeting any of the following criteria will not be eligible for participation in the study:

1. Investigational therapy within 4 weeks prior to CMB305 dosing
2. Prior administration of other NY-ESO-1-targeting immunotherapeutics
3. Prior treatment with immune checkpoint therapies, including anti-CTLA-4, anti PD-1, and anti PD-L1 therapeutic antibodies, or any other antibody or drug targeting T cell costimulation
4. Treatment with systemic immunostimulatory agents (including but not limited to IL-2) within 4 weeks or five half-lives of the drug, whichever is shorter, prior to first dose
5. Significant immunosuppression from:
 - a. Concurrent, recent (≤ 3 weeks prior to the first schedule dosing) or anticipated need for treatment with systemic corticosteroids (the use of physiologic doses of corticosteroids may be approved after consultation with the Sponsor). The use of topical or inhaled corticosteroids and mineralocorticoids (e.g., fludrocortisone) is allowed.
 - b. Other immunosuppressive medications (≤ 3 weeks prior to the first scheduled dosing) including but not limited to cyclophosphamide, azathioprine, methotrexate, thalidomide, and anti-tumor necrosis factor (anti-TNF) agents or conditions such as common variable hypogammaglobulinemia.
6. Other cancer therapies, including chemotherapy, radiation, biologics or kinase inhibitors within 3 weeks prior to the first scheduled dosing
7. Has received colony stimulating factors (CSFs; including granulocyte [G]-CSF, granulocyte-macrophage [GM]-CSF, or recombinant erythropoietin) within 4 weeks prior to the first scheduled dosing
8. Psychiatric, other medical illness, or other condition that in the opinion of the Investigator prevents compliance with study procedures or ability to provide valid informed consent
9. History of autoimmune disease, including but not limited to myasthenia gravis, myositis, autoimmune hepatitis, systemic lupus erythematosus, rheumatoid arthritis, inflammatory bowel disease, vascular thrombosis associated with antiphospholipid syndrome, Wegener's granulomatosis, Sjögren's syndrome, Guillain-Barré syndrome, multiple sclerosis, vasculitis, or glomerulonephritis (see [Appendix E](#) for a more comprehensive list of autoimmune diseases)
 - Patients with a history of autoimmune-related hypothyroidism on a stable dose of thyroid replacement hormone may be eligible for this study.
 - Patients with controlled Type 1 diabetes mellitus on a stable insulin regimen may be eligible for this study.
10. History of idiopathic pulmonary fibrosis (including pneumonitis), drug-induced pneumonitis, organizing pneumonia (i.e., bronchiolitis obliterans, cryptogenic organizing pneumonia), risk of pulmonary toxicity, or evidence of active pneumonitis on screening chest CT scan. History of radiation pneumonitis in the radiation field (fibrosis) is permitted.

11. Significant cardiovascular disease, such as New York Heart Association cardiac disease (\geq Class II), myocardial infarction within the previous 3 months prior to study treatment, unstable arrhythmias, or unstable angina
12. Inadequate organ function, including the following:
 - a. Marrow: ANC \leq 1500/mm³, platelets $<$ 75,000/mm³, or hemoglobin (Hb) $<$ 10 g/dL
 - b. Hepatic: ALT, and AST $>$ 2.5 \times ULN (OR \geq 5 \times ULN for subjects with liver metastases), total serum bilirubin $>$ 1.5 \times ULN (OR direct bilirubin \geq ULN for patients with total bilirubin levels $<$ 1.5 \times ULN; patients with Gilbert's Disease may be included if their total bilirubin is $<$ 3.0 mg/dL)
 - c. Renal: creatinine $>$ 1.5 \times ULN
 - d. Other: prothrombin time (PT), international normalized ratio (INR), or partial thromboplastin time (PTT) $>$ 1.5 \times ULN
13. Uncontrolled pleural effusion, pericardial effusion, or ascites requiring recurrent drainage procedures (once monthly or more frequently). Patients with indwelling catheters (e.g., PleurX[®]) are allowed.
14. Uncontrolled tumor-related pain. Patients requiring pain medication must be on a stable regimen at study entry. Symptomatic lesions amenable to palliative radiotherapy (e.g., bone metastases or metastases causing nerve impingement) should be treated prior to enrollment. Asymptomatic metastatic lesions whose further growth would likely cause functional deficits or intractable pain (e.g., epidural metastasis that is not presently associated with spinal cord compression) should be considered for loco-regional therapy if appropriate prior to enrollment.
15. Uncontrolled hypercalcemia ($>$ 1.5 mmol/L ionized calcium (Ca) or Ca $>$ 12 mg/dL or corrected serum calcium $>$ ULN) or symptomatic hypercalcemia requiring continued use of bisphosphonate therapy or denosumab. Patients who are receiving these agents specifically to prevent skeletal events and who do not have a history of clinically significant hypercalcemia are eligible. Patients who are receiving denosumab prior to enrollment must be willing and eligible to discontinue its use while on study and receive a bisphosphonate instead.
16. History of other cancer within 3 years (except for appropriately treated carcinoma in situ of the cervix, non-melanoma skin carcinoma, Stage I uterine cancer, localized prostate cancer treated with curative intent, ductal carcinoma in situ treated surgically with curative intent, or other cancers with a similar outcome)
17. Evidence of active tuberculosis or recent ($<$ 1 week prior to first scheduled dosing) clinically significant infection requiring systemic therapy (prophylactic antibiotics [e.g., for prevention of a urinary tract infection or chronic obstructive pulmonary disease] are permitted)
18. Evidence of active hepatitis B (HepB), hepatitis C (HepC), or Human Immunodeficiency Virus (HIV) infection. Active HepB is defined as having a positive HepB surface antigen (HBsAg) test at screening. Patients with past/resolved HepB viral infection (defined as having a negative HBsAg test and a positive antibody to HepB core antigen [anti-HBc] antibody test) are eligible. HepB viral DNA must be negative in these patients prior to the

first scheduled dosing. Patients positive for HepC antibody are only eligible if polymerase chain reaction (PCR) is negative for HepC viral RNA.

19. Administration of a live, attenuated vaccine within 4 weeks prior to the first scheduled dosing or anticipation that such a live attenuated vaccine will be required during the study. Influenza vaccination should be given during influenza season only (approximately October to March). Patients must not receive live, attenuated influenza vaccine (e.g., FluMist[®]) within 4 weeks prior to the first scheduled dosing or at any time during the study.
20. Known active or untreated central nervous system (CNS) metastases. Patients with a history of treated asymptomatic CNS metastases are eligible, provided they meet all of the following criteria:
 - a. No metastases to cerebellum, brain stem, midbrain, pons, medulla, or within 10 mm of the optic apparatus (optic nerves and chiasm)
 - b. No evidence of interim progression ≥ 4 weeks between the completion of CNS-directed therapy and the screening radiographic study and ≥ 2 weeks since discontinuation of corticosteroids
 - c. No ongoing requirement for dexamethasone as therapy for CNS disease; anticonvulsants at a stable dose allowed
21. Pregnant, planning to become pregnant within 6 months of treatment, or nursing
22. Known allergy(ies) to any component of CMB305, atezolizumab, or severe allergic reactions to monoclonal antibodies, fusion proteins, or CHO cell products

